3. RESEARCH METHODS

3.1 Phase 1 pilot study.

The 12 month pilot study is already funded through the NIHR Primary Care School and is taking place in two Southampton area and two Oxford area practices over the coming Autumn/ Winter seasons of 2009/10. It is due to complete in April-July 2010. It is being performed because this is the first study of its type in primary care. We are using a moderate degree of new technology, *e.g.* tympanometry and a new mechanical technique for treatment in this setting. Also the new research practices require full training with the specific study material packages. The pilot aims for 28 children. We currently estimate uptake rates of 40% which we deem likely because all children confirmed with symptomatic and tympanometric OME will be offered a treatment and improved monitoring in addition to usual care (also there are no known side effects to this treatment). Basing the take-up on 40%, 112 children accepting screening from 280 invited through 4 practices, 25% of which will be eligible for randomisation on tympanometry will yield 28 children in the pilot trial. This pilot will allow confirmation of the trial uptake estimates of 40% with a 95% level of precision of ± 5.7%.

3.1.1 Progress with the pilot study

The necessary National Research Ethics Service full approval for both the pilot and main study has been received on the 10th August 2009 Ref 09/ H0504/75. All trial materials have been developed (including the manual) and adapted awaiting further operational feedback. Research Governance approval has also been given for phases 1 and 2; and the 4 practice training sessions with research nurses and teams have been completed this month (September 09). Supplies (100 packs) have been received from the company and have been distributed to the practices. We have obtained some preliminary parent feedback about use of autoinflation via company consumer feedback. A website (Otovent) http://www.gluear.co.uk supplies accurate patient information about using the balloons and has a high quality demonstration video (also available on You-Tube). A participant forum and FAQ are also on this website. We will recommend initial access to this site in the intervention arm, and for controls wishing to use it at 3 months.

3.1.2 Completed pilot study summary

The pilot work has i) demonstrated feasibility ii) demonstrated good study compliance with the technique and follow up iii) improved logistical assumptions e.g. trial uptake precision estimates, iv) provided useful consumer feedback, v) developed the study materials and information in a standard operating manual, vi) confirmed the original study power calculation and demonstrated a potential large effect size OR 4 95%CI 0.97 to 16.46, vii) added a new exclusion criterion viii) refined the randomisation method to be used to improve access- now web based with training support ix) developed a web based hearing disability outcome with evaluation of reliability for use as a trial outcome x) improved the trial management structure and costings.

3.2 Phase 2. Main Study

An open two arm randomised control trial of autoinflation in the treatment of OME in 4-11 year old children with assessment of effectiveness and cost-effectiveness at 1 month and 3 months (this application).

A large randomised pragmatic trial is needed to establish objectively short term clinical effectiveness (not known) and cost effectiveness at one month, and important NHS effectiveness and cost-effectiveness outcomes in the medium term at 3 months. This is both a usual and expedient time frame for the many children with OME episodes who are initially managed in primary care (we will use scenarios for longer term cost estimates). 11,15,20

3.2.1 Setting

The research will be based in the community. The study will complete the pilot in Thames Valley, Hampshire, and Wiltshire regions first. The main study will be set within 40 GP practices; 20 each around the Southampton and Oxford centres. The GPs in each practice will act as the Principal Investigators and a Research Nurse will be assigned to each practice if one is not already in place. Practices will be recruited through the South West and South East Primary Care Research Networks.

3.2,2 Target population

Children aged 4-11 years, attending or just about to attend school will be identified through four routes:-

- 1. Parents of all children at increased risk of OME i.e. those aged 4, 5 and 6 years (high prevalence of OME, 10-30%)⁸ will be identified from practice age sex registers, and will be sent an invitation letter and information sheet in the autumn in time to coincide with the high seasonal prevalence. The letter and information sheet will describe glue-ear and the symptoms it commonly produces. Where there are no specific OME related concerns in the past 3 months (highlighted on the invitation letter checklist) parents/guardians will be advised that a screening is not_required. The letter will detail the purpose of the study, what it entails etc. and offer interested parents of symptomatic children up to two tympanometric screenings, one in the first or autumn term (Sept Dec) and for those passing the tympanometry at this time (i.e. do not have at least one B reading) a second screen offer will be made for the spring term (Jan Apr). Should asymptomatic children go on to develop suggestive symptoms over the study period e.g. develop an ear infection, hearing or speech concerns etc. an opportunistic screening will be arranged directly.
- 2. A Research Nurse (RN) will audit the notes of all 7-11 year old children using Read codes to identify those having attended the practice with any ear related problems in the previous year. These children will then be invited for a targeted screen using an appropriate invitation letter to guardian and child (checking not to duplicate invitation).
- 3. A clinical opportunistic case finding approach will be used where each participating practice will be alerted to the ongoing study and all GPs, nurses, health visitors etc will refer on suspected new cases to the research nurse.
- 4. Links may be made with the local school nurses for any suspected participating practice registered incident cases they see to be informed about the study.

3.2.3 Recruitment procedures (see Appendices 1 and 2)

For parents accepting the invitation for screening of their children, the research nurse will make an appointment for them and their child to be seen. At this initial appointment the research nurse will go through the study and information sheet, answer any questions etc. Full informed consent will then be taken for those parents wishing their child to be screened, and assent will be taken from the children. (Information sheets and consent/assent forms will be used for each age group; 4-6 years old and 7+ year olds).

The research nurse will first use otoscopy (we will ensure access to good quality otoscopes) to check for any obstructing wax, perforations etc., before performing the tympanometry on both ears. The modified Jerger classification will be used. ^{15,34,35} The findings will be explained to the parents and children, and any child with a relevant symptom history and at least one ear with a B tympanogram will be invited to take part in the study. Those wishing to participate will be randomised 50:50 by a web based randomisation method to either standard care by their practice (*i.e.* the usual care unaffected by being in the study) plus autoinflation for 1 to 3 months, or standard care alone by their practice for 3 months. It will be explained to the standard care only group that if after three months their child's ears have not got any better (estimate about 50% chance of cure overall for uni and bilateral cases combined by 3 months in controls) ¹⁵ they can receive autoinflation if they so

wish (for trial follow -up period 3-6 months). This as previously stated, should improve recruitment rates into the study, which have been refined by the pilot, and should furthermore encourage the active monitoring process for control children up to 3 months including those where there is no initial resolution at 1 month. Parents from each arm will be asked to complete the OMQ-14 functional health status questionnaire that bests predicts QoL (to assess baseline severity in a standardised manner), and also complete a short studyspecific questionnaire. The participants will also be given a weekly symptom diary to complete (for 1 month at the first visit, and 2 months at the second visit). Symptom diaries are based on measures developed in the GNOME study and a previous Acute Otitis Media study. 15,36 Parents will also receive a daily check sheet to complete with their child to assess compliance, record ease of use and provide details of what treatment, if any they have used (see also outcomes section). NRES has suggested giving tokens for children as a reward e.g. Waterstones/HMV tokens, which both groups will receive at 1 and 3 months for returned completed diaries (£7.50 each, total £15), and should also help somewhat to offset travel etc. for families and so improve compliance. Hearing disability will be evaluated at baseline, and 1 month. Pure tone audiometry is not likely to be valid in the usual primary care setting, and history for hearing loss is only 71% sensitive. 11,15,37 Therefore nurses will instruct on use of a web based test: a forced choice two alternative auditory disability and speech reception test (TADAST), which is less prone to invalidation by back ground noise, is already in a standardised format, and was originally developed in primary care to assess children with glue ear.³⁸ The pilot has shown good test-retest repeatability of this new web version in 4-11 year old children (medical student project 2010).

Children randomised to receive autoinflation will be shown by the research nurse how to perform autoinflation. The guardian will also be involved to demonstrate use of the balloon for the child to copy, to improve compliance. When the balloon has thus been stretched sufficiently through use, the child will be encouraged to blow up the balloon for themselves, firstly through the mouth, then by blowing out through their nose. Recipients will be provided with the nasal fitting device, with 5 balloons per trial intervention pack, containing pictorial and written instructions on correct use. Additional website and You-Tube address details will be supplied so that children and parents can watch a video of the method whenever they choose, to provide support on correct performance of the technique. Micro-tympanometry will also be done immediately after per-nasal inflation of the balloon to record the tympanogram type, either A, C1, C2, or B (a sequence of increasing severity). This is being done to see if any immediate conversion of tympanogram type to one of improved middle ear pressure predicts results at 1 month. Parents will be phoned at home by the nurse after 2-4 days, primarily as a supportive measure with the nurse providing any additional requested information for parents and children that should also encourage compliance. The nurse will take note of any untoward effects and discuss any queries or issues. Where compliance is reported as unsatisfactory a second nurse appointment will be offered, when the child and guardian can be given further specific pragmatic tips and education about improving the technique based directly on observation of use. ([name] has provided useful practical advice on procedures which we have implemented in the pilot). After 1 month those not cured using tympanometric criteria in the intervention arm will be encouraged to use a further 2 months course of balloons for autoinflation, supplied in 2 boxes.

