8.2 Statistical Analysis

The main analysis will be an intention to treat analysis with individual children the unit of analysis rather than ears. Proportions of children cleared of one or more B type tympanograms (90% probability of effusion) at 1 month will be compared using a logistic regression model adjusting for the variables used in minimisation and other covariates as appropriate (including likely effect modifiers). Although not specifically powered to assess effect modification we will explore potentially important variables: interaction tests will be performed between randomisation groups and if statistically significant, subgroup results will be presented separately. From the GNOME trial only clinical severity was an effect modifier, however two interesting subgroups were noted on secondary analysis relating to age as a dichotomous outcome (>=6.5 years versus <6.5 years) and gender. Season and atopic status were not effect modifiers. Severity will include tympanogram readings (unilateral versus bilateral effusion), frequency of GP surgery attendance in the past 12 months for ear problems, and OMQ-14 score at baseline.

Logistic regression models will also be used for other dichotomous outcomes, and ANCOVA will be used for continuous variables adjusting for baseline differences and potential effect modifiers as appropriate. All estimates will be presented with 95%C.I.s. A trial analysis plan will be drawn up before the main trial starts.

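### Section 3.2.3 describes the parent-completed baseline OMQ-14 after allocation in an open trial, and no visible text requires it to come first

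*Protocol*

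**What the plan says.** Section 3.2.3 goes through consent, otoscopy and tympanometry, and then states: "Those wishing to participate will be randomised 50:50 by a web based randomisation method to either standard care by their practice" with or without autoinflation. Next comes what control families are told: "It will be explained to the standard care only group that if after three months" the ears are no better, they can have the device. Only after that does the text say: "Parents from each arm will be asked to complete the OMQ-14 functional health status questionnaire that bests predicts QoL (to assess baseline severity". Parents are to do this "and also complete a short studyspecific questionnaire".

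The other places that bear on timing do not fix the order:

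- Section 3.2.4 makes the nurse's judgement that the child can probably use the device a condition of being offered randomisation. It does not mention completed baseline forms.
- Section 7.2 lists the OMQ-14 as self-administered at baseline and 3 months and points to Appendix 2.
- Section 8.3 lists the Health Utilities Index (HUI), answered by parents or carers as proxies, at baseline, 1 and 3 months.

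Section 3.3 says that blinding is not possible. Section 8.2 says "ANCOVA will be used for continuous variables adjusting for baseline differences" and potential effect modifiers. It names the baseline OMQ-14 score as one of three severity measures, and it lets likely effect modifiers enter the primary logistic model as appropriate.

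**The concern.** A baseline covariate is safe to adjust for because allocation cannot have influenced it. If a parent rates the child's last three months after learning that the device starts today, or that it will be withheld for three months, that protection is lost. The score then partly reflects the allocation, and adjusting for it can create a difference between arms that randomisation would otherwise have prevented.

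The protocol's defence against subjective bias in section 3.3 is its objective tympanometric outcome. That does not protect a parent-completed questionnaire. The analyses exposed are the ANCOVA of the 3-month OMQ-14, any interaction test that uses baseline OMQ-14, and the primary model if OMQ-14 is chosen as a covariate. The baseline HUI, which enters the QALY calculation, would be exposed in the same way if it were collected after allocation, but section 3.2.3 does not mention it.

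**Working it through.** **Order of events in the text**

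| Order of mention | Step | Place |
|---|---|---|
| 1 | Consent, otoscopy, tympanometry | 3.2.3 |
| 2 | Web randomisation 1:1 | 3.2.3 |
| 3 | Explanation to the control group | 3.2.3 |
| 4 | OMQ-14 and study questionnaire from parents in each arm | 3.2.3 |
| 5 | Baseline hearing disability test (TADAST) | 3.2.3 |
| 6 | Device training for those allocated to it | 3.2.3 |

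Step 4 speaks of parents by arm. A nurse who followed the text literally would randomise first.

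**What is fixed before allocation.** Eligibility rests on symptom history and a B tympanogram. The minimisation factors in 3.2.4 are age, one versus two B tympanograms, and gender. None of them uses the OMQ-14.

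**What uses the baseline OMQ-14.** Section 8.2 names it as a severity measure for effect modification. It is the obvious baseline for the 3-month OMQ-14, although 8.2 does not list covariates outcome by outcome. It enters the primary model only if selected.

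**Size, for illustration.** The concern rests on no figure in the protocol. Two inputs come from section 8.1: 125 children per arm, and a target of about 0.3 SD on continuous measures, with the OMQ-14 total given as an example. The other two are assumptions with no support in the documents:

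- s, the shift in mean baseline score between arms caused by knowing the arm: 0, 0.1 or 0.2 SD.
- b, the slope of follow-up on baseline in SD units, equal to the correlation when both have SD 1: 0.5 or 0.7.

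The calculation also assumes no true effect and no influence of the arm on the follow-up rating.

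- Bias of the adjusted difference = b × s.
- Standard error = √(1 − b²) × √(2/125). This is 0.866 × 0.1265 = 0.110 for b = 0.5, and 0.714 × 0.1265 = 0.090 for b = 0.7.
- Two-sided rejection rate at a nominal 5% = 1 − Φ(1.96 − bias/SE) + Φ(−1.96 − bias/SE).

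| s (SD) | b | Bias (SD) | Share of 0.3 SD | Type I error |
|---|---|---|---|---|
| 0 | either | 0 | 0% | 5% |
| 0.1 | 0.5 | 0.05 | 17% | 7.4% |
| 0.1 | 0.7 | 0.07 | 23% | 12.1% |
| 0.2 | 0.5 | 0.10 | 33% | 15.0% |
| 0.2 | 0.7 | 0.14 | 47% | 34.1% |

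**HUI.** Section 8.3 uses area under the curve over 0, 1 and 3 months. Assuming straight lines between the points, baseline has weight 0.5 month out of 3, or one sixth.

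**Sample size.** The order of the forms does not enter the calculation. The 250 evaluable children and 250/0.85 = 294.1, rounded up to 295, are unchanged.

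**The case against.** The strongest reply is that the order of the text is not the order of the visit. Section 3.2.3 is partly arranged by topic: it moves from the OMQ-14 to diaries and tokens at later visits, then back to hearing at baseline. Section 3.2.4 describes the assessment that precedes the offer of randomisation only after device training and the follow-up call have been covered. The reference to each arm may simply mean that both groups complete the form. Section 7.2 sends the reader to Appendix 2 for the OMQ-14, that flow chart is not shown, and the protocol also mentions a trial manual. All of this stands. The order is an inference, and the charts may already put the forms first. If they do, the text still has to be brought into line with them.

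The limits on scope also stand. The study questionnaire is not named as a covariate or effect modifier. For the HUI the point rests only on silence about its timing, its baseline weight is small, and section 8.3 allows regression control for baseline differences. The TADAST is a forced-choice performance test, so the argument about parental rating does not carry over to it. Recall over three months may dampen any shift.

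A reader might go further and infer that the forms will certainly be completed after allocation, or that the primary result is biased. The documents support neither. No sentence places the forms after randomisation in so many words, and the primary outcome, the eligibility test and the minimisation factors do not depend on the OMQ-14.

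**Conclusion.** The point holds as a gap in a procedure that the protocol itself describes. The visible text puts a parent-rated baseline after allocation, in an open trial, and nothing visible requires the reverse. What is exposed is the adjusted analysis of the 3-month OMQ-14, the exploratory interaction with baseline OMQ-14, and the primary model only if OMQ-14 is added to it. The unadjusted tympanometric comparison is untouched.

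Under the assumed shift and slope the bias runs from 0 to 0.14 SD, at most 47% of the protocol's target of about 0.3 SD. These figures show what such a shift would do; they are not evidence that one would occur. The direction cannot be predicted, since either arm might rate worse and arm-influenced rating at follow-up could add to the bias or partly offset it. It could not be reliably corrected afterwards, which is the reason to close the gap in advance.

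**What to change.** State in sections 3.2.3 and 3.2.4 that, once a B tympanogram is confirmed and the family has agreed to take part, the parent-rated baseline forms (OMQ-14, study questionnaire and baseline HUI) are completed at the entry visit before the randomisation website is opened. Add a field to the web form in which the nurse confirms this before the allocation is shown. Check Appendix 2 and make text and chart agree.

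Do the baseline TADAST before allocation where feasible, but do not make it a condition of allocation. It is a web test that families complete themselves under parental supervision, the protocol does not say that it is finished at the visit, and waiting for it could delay randomisation.

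The cost is slightly more time before allocation and one extra web field, to be arranged with the external agency that provides the website. Instruments and sample size do not change. If practices already work in this order, the edit only records it.

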3.2.4 Randomisation

If the trained research nurse assesses that the child is likely to be able to use the device they will be offered randomisation. To ensure the generator and executor processes are fully independent in relation to randomisation (and avoid subversion) we will employ an external agency to provide a web-based randomised selection method to participating trial nurses who will access a preloaded website on their computer. Nurses will be trained in use of the website and have further access to support. Randomisation will be overseen by the Primary Care Clinical Trial Unit located at Oxford. A standard minimisation protocol will be used based on three potentially important variables: age (>=6.5 years versus <6.5 years); baseline severity (1 versus 2 B type tympanograms); and gender. 15

3.3 Justification of an open pragmatic trial

Because of the nature of the procedure use of a placebo and blinding are not possible. However effectiveness outcomes for the NHS are best measured by such a method, and will reflect real life outcomes. The use of an objective primary outcome - tympanometric cure, one that is also independently verifiable, will reduce potential subjective biases in the study. We will use faxes of tympanograms to the main co-ordinating centre to improve validity of this outcome and check correct categorisation of baseline, one and three month recordings. We will estimate placebo effects of using the device by asking how effective parents and children believed the device to be at 2-4 days.

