4. ETHICAL ARRANGEMENTS

This trial aims specifically to improve child health for this group of children and to establish the best non-surgical treatment for children with OME. Children are the main "consumer" group suffering from OME and its protracted effects, so adult studies (with a different aetiology and natural history) are inappropriate. As this trial will randomly allocate an additional treatment with preliminary evidence of effectiveness for the patient's condition as an adjunct to standard care, there will be no compromise of their care from the NHS. Trial support for clinical care with improved diagnostic monitoring should ensure exemplary clinical management during the NICE recommended active monitoring period (3 months).¹¹

A qualified research nurse, used to working with children, will be given specific training in the trial protocol and will be provided with the trial manual. They will conduct all the trial procedures e.g. interviews and assessments, provide instructions etc. which will be minimally invasive (e.g. otoscopy, micro- tympanometry, web hearing disability test, study questionnaires). All trial staff (Research Nurses, Principal Investigators, the Chief Investigator and Trial Manager) will attend an approved ICH-Good Clinical Practice training session if they have not received training within the year prior to the main trial commencement date.

Children will only be involved after full informed consent is given. In accordance with National Research Ethics Service (NRES) guidance 6-11 year olds will be asked to give their assent after their parent/guardian has given consent. For the younger children (4-5 year olds) only the parent/guardian will be asked for consent, and no assent will be sought from these children. If a child refuses to participate or carry on, once consented into the trial their decision will always be respected. No pressure will be exerted on a child or their parent/guardian to participate nor will they receive financial benefit other than modestly priced book tokens for completing the diaries. There are several approved trial information sheets: a detailed one for the parents/guardians; one for 6-11 year olds and one for 4-5 year olds.

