7. OUTCOME MEASURES

7.1 Main outcome

The primary outcome will be a tympanometric measure. Tympanometric resolution in ears will be defined as conversion of the B-type highly predictive of effusion to either an A or C1 type i.e. back to normal pressures. Type C2 will not be considered sufficiently cured or resolved because the PPV for effusion of C2 remains modest at 55%.³⁴

The difference in proportions of children showing resolution to A or C1 in at least one B (affected) ear per child at one month is the main study outcome.

This outcome is chosen based on evidence from the Cochrane review and hence is the basis for the sample size calculation. It is also a robust outcome and less likely to be affected by any placebo effect of intervention. Otoscopy will be performed by the trained nurse prior to tympanometry to improve method validity. Nurses will attend a day course that includes full relevant instruction in practical tympanometry procedures and will use a learning-set of tympanogram print outs to categorise type before collecting data as a training aid. The MTP-10 micro-tympanometers used (sufficient stock is available from the recent GNOME trial) are being serially re-calibrated for the proposed new trial and all have a print out facility. A central trial fax-hotline will be used for tympanogram interpretation in the study for "at-point-of-care" support, and will be the basis for continuing training of operators to improve repeatability and validity of the method. (Tympanometric skills will be assessed in initial samples of consecutive cases per nurse-operator).

Difference in tympanometric baseline severity is likely to be an effect modifier and will be accounted for in both the minimisation protocol and secondary analysis (see relevant sections).

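### The planned central check of faxed tympanograms is not stated to be masked to arm, nor to supply the primary outcome reading

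*Protocol*

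**What the plan says.** Section 3.3 of the protocol defends the open design with the sentence "Because of the nature of the procedure use of a placebo and blinding are not possible". It then relies on an objective primary outcome that can be verified independently. To support that, it says "We will use faxes of tympanograms to the main co-ordinating centre to improve validity of this outcome" and that the centre will "check correct categorisation of baseline, one and three month recordings".

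Section 7.1 gives the fax line a second role: "A central trial fax-hotline will be used for tympanogram interpretation in the study", described there as point-of-care support and as a basis for continuing operator training. The same section defines success at 1 month as conversion from type B to type A or C1 in at least one affected ear; C2 does not count.

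On who takes the readings, section 4 says of the research nurse: "They will conduct all the trial procedures e.g. interviews and assessments, provide instructions etc". Micro-tympanometry is among the procedures listed. Section 7.1 says that nurses "will use a learning-set of tympanogram print outs to categorise type before collecting data as a training aid". Under sections 3.2.3 and 3.2.4 the research nurse also obtains the web randomisation, teaches the device to intervention children, telephones their families and re-coaches technique where compliance is poor.

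**The concern.** The blinding sentence does not separate three groups: the families, the nurses who deliver the intervention, and the person who assigns a type to a printed trace. The first two cannot be blinded. The third can, because the tympanometers print their traces and the protocol already sends traces to the centre.

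The point matters because the endpoint depends on a category boundary. A trace near the C1/C2 border is a success or a failure according to the type assigned. Only one affected ear need convert, so in a bilateral case one reading can decide the child's outcome. If the reader knows the arm, borderline traces can drift in different directions in the two groups, which biases the treatment comparison.

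The protocol's answer to the bias of an open trial is the objectivity of this outcome. That answer is strongest if the reading that counts is made without knowledge of allocation, and the protocol does not say that it is. Section 7.1 does argue that the outcome is less open to a placebo effect, but that concerns the child's response, not the reader.

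**Working it through.** **1. What the text fixes about the reading**

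- Initial reader: the research nurse (sections 4 and 7.1), who knows the arm (sections 3.2.3 and 3.2.4).
- Central step: a check of categorisation at three visits (section 3.3), plus live interpretation support and training (section 7.1).
- Masking of the central reader: not stated.
- Which reading is analysed, and how disagreement is settled: not stated.

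**2. The plan's own figures (section 8.1)**

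Inputs: control resolution 45%, odds ratio 2.4, alpha 5% (taken as two-sided; the protocol does not say), power 90%, 15% loss.

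- Intervention odds = 2.4 × 0.45/0.55 = 1.964, so the intervention proportion = 1.964/2.964 = 0.663.
- The two-proportion formula with continuity correction gives 122 per arm, or 244 in total. The stated figure is 250 (125 per arm), within 3%.
- 250/0.85 = 294.1, rounded up to the stated 295.

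The plan's figures are therefore reproduced closely enough to use 125 per arm below.

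**3. Effect of differential misreading when there is no true effect**

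The bias values b are assumptions; nothing in the protocol gives them. Each is the net difference between arms left after any central correction. The calculation uses an unadjusted comparison of proportions.

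- SE = √(2 × 0.45 × 0.55/125) = 0.0629.
- Two-sided type I error = P(|Z + b/SE| > 1.96).

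| Assumed net bias b | Children per 125 | b/SE | Type I error |
|---|---|---|---|
| 0 | 0 | 0 | 5% |
| 3 points | 3.75 | 0.48 | 7.6% |
| 5 points | 6.25 | 0.79 | 12.5% |
| 8 points | 10 | 1.27 | 24.6% |

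**4. Could misreading create the whole planned effect?**

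If only unresolved intervention children were misread as resolved, moving 45% to 66.3% would need (0.6626 − 0.45)/0.55 = 0.387, so about 39% of them misread. That is not plausible.

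Under the same one-directional assumption, misreading 2%, 5% or 10% of unresolved intervention children gives an apparent odds ratio of 1.05, 1.12 or 1.25. The chance of a false significant benefit is then about 3.7%, 6.4% or 13.8%, against a nominal 2.5% in that direction.

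**5. Effect of the fix on sample size**

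None. Masked reading leaves 250 evaluable and 295 randomised.

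**The case against.** The best defence is that the blinding sentence is about the procedure, meaning those who give and receive the balloon, and is right about them. The outcome is recorded by an instrument. Nurses train on a learning set and their skills are assessed on initial consecutive cases. The centre checks the categorisation at all three visits, and a check of correctness implies that wrong categories can be put right.

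Much of this stands, and it limits the point in four ways.

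- A reader might infer that the nurse's category is the one analysed. The protocol does not say so; it is silent on which reading prevails.
- A reader might infer that the trial has no independent safeguard. It has one, because the central check is real. What is missing is masking of the checker and a rule on which reading counts.
- A reader might take it that every print-out is faxed. That is a fair inference from the three visits named in section 3.3, but the protocol does not use the word.
- A reader might take the type I error figures as estimates of bias in this trial. They are not: the 3, 5 and 8 points are all assumed, and they give no credit for training or central correction.

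The defence does not show that the check is masked or that it defines the outcome. Masked assessment is a matter of design and data collection, and section 3.3 is where the protocol deals with it. It cannot be left to an analysis plan, because it has to be in place when the traces are read.

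**Conclusion.** The point holds as a gap. Section 3.3 treats blinding as impossible without setting apart the reader of a printed trace. The central check is not stated to be masked, and no reading is named as the primary outcome.

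The likely consequence is moderate: an inflated estimate, or a false positive at an effect smaller than planned. On the assumed net biases of 3 to 8 points, the type I error would be about 7.6% to 24.6%. These figures rest on 45% resolution in both arms, 125 evaluable children per arm, a two-sided 5% test and an unadjusted comparison. The protocol does not support the conclusion that misreading could by itself generate an odds ratio of 2.4.

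This should be fixed. It is a cheap improvement rather than a fatal flaw, because a partial safeguard already exists.

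**What to change.** Amend sections 3.3 and 7.1 to state the following.

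- Families and treating nurses cannot be blinded, but the classification of the printed tympanograms will be.
- Baseline, 1-month and 3-month traces faxed for the existing central check carry study number and visit only, with nothing that shows allocation.
- The staff who already do that check classify the traces masked to arm, and this masked reading is the primary outcome.
- The nurse's reading is used on the day and in a sensitivity analysis, with nurse/centre disagreements reported.
- Hotline advice is kept separate and does not set the study reading.
- The trace taken immediately after inflation (section 3.2.3) is kept out of the masked set. Only intervention children have one, so it would reveal the arm.

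The cost is a cover-sheet rule, protocol wording and a way of keeping hotline contact apart from the masked reading. No procedure is added for children and the sample size does not change. The downsides are a short delay before a category is final and some disagreements to report. Masked reading also leaves one source of bias untouched: an unmasked nurse still acquires the trace and may choose which to repeat or send.
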